7.2. Secondary Pharmacodynamic Analyses

The secondary pharmacodynamic analyses will be conducted in the same manner as the primary pharmacodynamic analyses. The only difference is that the timepoint of interest is now PET2. The output corresponding to the secondary pharmacodynamic analysis will be obtained from the primary pharmacodynamic analysis and corresponds to PET2/Predose and PET2/PET1.

7.2.1. Endpoint / Variables

Changes in the uptake of [18 F]-FBA-A20FMDV2 in the whole lung (assessed as the V_T) up to PET2 post-dose compared to Pre-dose, as measured by PET.

7.2.2. Summary Measure

• Ratio (PET2/Pre-dose) in the volume of distribution (V_T), not corrected for air volume at 14-28 hrs post-dose as measured by PET.

7.2.3. Population of Interest

The secondary pharmacodynamic analyses will be based on the Per Protocol (PP) population, unless otherwise specified.

7.2.4. Strategy for Intercurrent (Post-Randomisation) Events

Treatment policy approach will be adopted hence the actual values of the endpoint regardless of whether the intercurrent event has occurred will be analysed as outlined in the primary pharmacodynamic analyses.

7.2.5. Statistical Analyses / Methods

Details of the planned displays are provided in Appendix 12: List of Data Displays and will be based on GSK data standards and statistical principles.

Unless otherwise specified, endpoints / variables defined in Section 7.2.1 will be summarised using descriptive statistics, graphically presented (where appropriate) and listed.

7.2.5.1. Statistical Methodology Specification

Endpoint / Variables

• V_T (whole lung, not corrected for air volume), at 1000 mcg GSK3008348

Timepoint

• The secondary timepoint of interest is the PET2.

Model Specification

• Similar to the primary pharmacodynamic analyses

Model Checking & Diagnostics

• Similar to the primary pharmacodynamic analyses

Model Results Presentation

• Similar to the primary pharmacodynamic analyses

Subgroup Analyses

• Similar to the primary pharmacodynamic analyses

Sensitivity and Supportive Analyses

• Similar to the primary pharmacodynamic analyses

7.3. Exploratory Pharmacodynamic Analyses

There are four exploratory objectives and associated endpoints as outlined Section 2.2. For the exploratory pharmacodynamic analyses, only endpoints associated with the following objective will be described in this RAP:

• To explore the pharmacodynamic effects of single nebulised doses of GSK3008348 in IPF patients using additional PET analyses techniques

The following objectives and associated endpoints below will be described separately from this RAP:

- To explore the spatial distribution of the effects of single nebulised doses of GSK3008348 in IPF patients and to compare it to the spatial distribution of disease
- To explore pharmacodynamic effects of GSK3008348 in blood
- To explore potential biomarkers of IPF disease and/or treatment response

7.3.1. Endpoint / Variables

 Change in the uptake of [¹⁸F]-FBA-A20FMDV2 in the whole lung (assessed using standardised uptake values [SUV] and V_T, with and without correction for air and/or blood volume) at various time points post-dose (PET1 and PET2) compared to predose (Pre-dose), as measured by PET

7.3.2. Summary Measure

- Ratio (PET1/Pre-dose) in the volume of distribution (V_T), whole lung, corrected for air volume at approximately 30 mins post-dose as measured by PET.
- Ratio (PET2/Pre-dose) in the volume of distribution (V_T), whole lung, corrected for air volume at 14-28 hrs post-dose as measured by PET.
- Ratio (PET2/PET1) in the volume of distribution (V_T), whole lung, corrected for air volume at approximately 30 mins and 14-28 hrs post-dose as measured by PET.
- Ratio (PET1/Pre-dose) in the standardised uptake values (SUV), whole lung, not corrected for air volume) at approximately 30 mins post-dose as measured by PET.
- Ratio (PET2/Pre-dose) in the standardised uptake values (SUV), whole lung, not corrected for air volume at 14-28 hrs post-dose as measured by PET.
- Ratio (PET2/PET1) in the standardised uptake values (SUV), whole lung, not corrected for air volume at approximately 30 mins and 14-28 hrs post-dose as measured by PET.
- Ratio (PET1/Pre-dose) in the standardised uptake values (SUV), whole lung, corrected for air volume at approximately 30 mins post-dose as measured by PET.
- Ratio (PET2/Pre-dose) in the standardised uptake values (SUV), whole lung, corrected for air volume at 14-28 hrs post-dose as measured by PET.
- Ratio (PET2/PET1) in the standardised uptake values (SUV), whole lung, corrected for air volume at approximately 30 mins and 14-28 hrs post-dose as measured by PET.

7.3.3. Population of Interest

The exploratory pharmacodynamic analyses will be based on the Per Protocol (PP) population, unless otherwise specified.

7.3.4. Strategy for Intercurrent (Post-Randomisation) Events

Treatment policy approach will be adopted hence the actual values of the endpoint regardless of whether the intercurrent event has occurred will be analysed as outlined in the primary pharmacodynamic analyses.

7.3.5. Statistical Analyses / Methods

Details of the planned displays are provided in Appendix 12: List of Data Displays and will be based on GSK data standards and statistical principles.

Unless otherwise specified, endpoints/variables defined in Section 7.2.1 will be summarised using descriptive statistics, graphically presented (where appropriate) and listed.

7.3.5.1. Statistical Methodology Specification

Endpoint / Variables

- Volume of distribution (V_T), (whole lung, corrected for air volume) at approximately 30 mins post-dose as measured by PET.
- Volume of distribution (V_T), (whole lung, corrected for air volume) at 14-28 hrs post-dose as measured by PET.
- Standardised uptake values (SUV), (whole lung, not corrected for air volume) at approximately 30 mins post-dose as measured by PET.
- Standardised uptake values (SUV), (whole lung, not corrected for air volume) at 14-28 hrs post-dose as measured by PET.
- Standardised uptake values (SUV), (whole lung, corrected for air volume) at approximately 30 mins post-dose as measured by PET.
- Standardised uptake values (SUV), (whole lung, corrected for air volume) at 14-28 hrs post-dose as measured by PET.

Timepoints

• The exploratory timepoints of interest are PET1 and PET2.

Model Specification

• Similar to the primary pharmacodynamic analyses

Model Checking & Diagnostics

• Similar to the primary pharmacodynamic analyses

Model Results Presentation

• Similar to the primary pharmacodynamic analyses

Subgroup Analyses

• None

Sensitivity and Supportive Analyses

• Similar to the primary pharmacodynamic analyses

8. SAFETY ANALYSES

The safety analyses will be based on the Intent-To-Treat (ITT) population, unless otherwise specified.

8.1. Adverse Events Analyses

Adverse events analyses including the analysis of adverse events (AEs), Serious (SAEs) and other significant AEs will be based on GSK Core Data Standards. The details of the planned displays are provided in Appendix 12: List of Data Displays.

8.2. Adverse Events of Special Interest Analyses

A comprehensive list of MedDRA terms based on clinical review will be used to identify each type of event. Changes to the MedDRA dictionary may occur between the start of the study and the time of reporting and/or emerging data from on-going studies may highlight additional adverse events of special interest, therefore the list of terms to be used for each event of interest and the specific events of interest will be based on the safety review by the study team in place at the time of reporting. The details of the planned displays are provided in Appendix 12: List of Data Displays.

8.3. Clinical Laboratory Analyses

Laboratory evaluations including the analyses of Chemistry laboratory tests, Haematology laboratory tests, Urinalysis, and liver function tests will be based on GSK Core Data Standards. The details of the planned displays are in Appendix 12: List of Data Displays.

8.4. Other Safety Analyses

The analyses of non-laboratory safety test results including ECGs, pulmonary function and vital signs will be based on GSK Core Data Standards, unless otherwise specified. The details of the planned displays are presented in Appendix 12: List of Data Displays.

9. PHARMACOKINETIC ANALYSES

9.1. Primary Pharmacokinetic Analyses

9.1.1. Endpoint / Variables

9.1.1.1. Drug Concentration Measures

Refer to Appendix 5: Data Display Standards & Handling Conventions (Section 15.5.3 Reporting Standards for Pharmacokinetic)

9.1.1.2. Derived Pharmacokinetic Parameters

Pharmacokinetic parameters will be calculated by standard non-compartmental analysis according to current working practices and using the currently supported version of WinNonlin. All calculations of non-compartmental parameters will be based on actual sampling times. Nominal sampling times may be used during any interim analysis. Pharmacokinetic parameters listed will be determined from the plasma concentration-time data, as data permits.

Parameter	Parameter Description			
AUC _(0-t)	Area under the concentration-time curve from time zero to the time of the last quantifiable concentration $(C(t))$ will be calculated using the linear trapezoidal rule for each incremental trapezoid and the log trapezoidal rule for each decremental trapezoid.			
AUC _(0-t) /D	AUC _(0-t) corrected for dose			
AUC _(0-inf)	Area under the concentration-time curve extrapolated to infinity will be calculated as: $AUC = AUC_{(0-t)} + C(t) / lambda_z$			
AUC _(0-inf) /D	AUC _(0-inf) corrected for dose			
C _{max}	Maximum observed concentration, determined from the concentration-time data.			
T _{max}	Time to reach C_{max} , determined directly from the concentration-time data.			
C _{max} /D	C _{max} corrected for dose			
Lambda_z ^[1]	The first order rate constant associated with the terminal (log-linear) portion of the concentration-time curve.			
Lambda_z_lower	First time point used in computing Lambda_z.			
Lambda_z_upper	Last time point used in computing Lambda_z.			
#pts	Number of points used in computing Lambda_z.			
r-squared	R-squared of Lambda_z computation.			
t ¹ / ₂	Apparent terminal half-life will be calculated as: $t\frac{1}{2} = \ln 2$ / Lambda_z			

NOTES:

• Additional parameters may be included as required.

9.1.2. Summary Measure

PK treatment comparisons are not planned for this study.

9.1.3. Population of Interest

The primary pharmacokinetic analyses will be based on the Pharmacokinetic population, unless otherwise specified.

9.1.4. Strategy for Intercurrent (Post-Randomisation) Events

In the event of a missing time point, PK parameters will be estimated from the available data on that day, unless the missing value compromises the accurate estimate of the parameter.

9.1.5. Statistical Analyses / Methods

Details of the planned displays are provided in Appendix 12: List of Data Displays and will be based on GSK Data Standards and statistical principles.

Unless otherwise specified, endpoints/variables defined in Section 9.1.1 will be summarised by period using descriptive statistics, graphically presented (where appropriate) and listed.

9.1.5.1. Statistical Methodology Specification

No formal statistical modelling will be performed, only descriptive statistics will be produced.

10. POPULATION PHARMACOKINETIC (POPPK) ANALYSES

Plasma concentration-time data may be used to derive population PK parameters/models using NONMEM or other currently validated software. The timeline for this analysis and reporting will be independent of the analysis described in this RAP. In an event that GSK3008348 is terminated before these analyses are conducted, they will not be reported.

11. BIOMARKER ANALYSES

Analyses for exploratory pharmacodynamic biomarkers of the $\alpha\nu\beta6/TGF\beta$ mechanism which may include but are not limited to: mRNA, microRNA and proteins in blood will be independent of the analysis described in this RAP and will be reported separately.

12. PHARMACODYNAMIC INTERIM ANALYSES

12.1. Pharmacodynamic Interim Analyses

The interim analysis for pharmacodynamics in Cohort 1 was based on the Per Protocol population.

The interim analysis was conducted in the same manner as the primary pharmacodynamic analysis and the primary timepoint of interest was the 30 minutes post-dose scan timepoint. The secondary timepoint of interest was the 14-28hrs post dose scan point. The data was reported to the study team with scrambled individual subject numbers.

12.1.1. Endpoint / Variables

- Change in the uptake of [¹⁸F]-FBA-A20FMDV2 in the whole lung (assessed as the volume of distribution [V_T], not corrected for air volume) at approximately 30 min post-dose compared to pre-dose, as measured by PET.
- Change in the uptake of [¹⁸F]-FBA-A20FMDV2 in the whole lung (assessed as the volume of distribution [V_T], not corrected for air volume) at 14-28hrs post-dose compared to pre-dose, as measured by PET.

12.1.2. Summary Measures

- Ratio (PET1/Pre-dose) in the volume of distribution (V_T), whole lung, not corrected for air volume at approximately 30 mins post-dose as measured by PET.
- Ratio (PET2/Pre-dose) in the volume of distribution (V_T), whole lung, not corrected for air volume at 14-28 hrs post-dose as measured by PET.
- Ratio (PET2/PET1) in the volume of distribution (V_T), whole lung, not corrected for air volume at approximately 30 mins and 14-28 hrs post-dose as measured by PET.

12.1.3. Population of Interest

The pharmacodynamics interim analyses were based on the Per Protocol (PP) population.

12.1.4. Strategy for Intercurrent (Post-Randomisation) Events

Treatment policy approach was adopted hence the actual values of the endpoint regardless of whether the intercurrent event had occurred were analysed as described for the primary pharmacodynamic analyses.

12.1.5. Statistical Analyses / Methods

Details of the planned displays were provided in Appendix 12: List of Data Displays and were based on GSK Data Standards and statistical principles.

Endpoints / variables defined in Section 12.1.1 were summarised using descriptive statistics, graphically presented (where appropriate) and listed.

12.1.5.1. Statistical Methodology Specification

Endpoint / Variables

- Change in the uptake of [¹⁸F]-FBA-A20FMDV2 in the whole lung (assessed as the volume of distribution [V_T], not corrected for air volume) at approximately 30 min post-dose compared to pre-dose, as measured by PET.
- Change in the uptake of [¹⁸F]-FBA-A20FMDV2 in the whole lung (assessed as the volume of distribution [V_T], not corrected for air volume) at 14-28hrs post-dose compared to pre-dose, as measured by PET.

Timepoints

- PET1.
- PET2

Model Specification

• Same model specifications as in Section 7.1.5.1 for the primary pharmacodynamics analyses

Model Checking & Diagnostics

• Same model specifications as in Section 7.1.5.1 for the primary pharmacodynamics analyses

Model Results Presentation

• Same model specifications as in Section 7.1.5.1 for the primary pharmacodynamics analyses

Subgroup Analyses

None

Sensitivity and Supportive Analyses

• Same model specifications as in Section 7.1.5.1 for the primary pharmacodynamics analyses

12.1.5.2. Table Illustrating Study Decision Making Used at Interim Analysis

	Interim outcomes from	Impact on development of				Cohort 2 -	Cohort- 2
	204715	GSK3008348	Traffic lights	Question for cohort 2	Cohort 2	Positive data	negative data
	No signal, variability as						
1)	expected	Stop development					
	Signal more variable than	Failure of PET					
	expected, sample size	endpoint not '348					
	increase required >10	continue to PD					
2)	subjects	study (pSMAD2)		N/A			
		Dependent on					
		number					
		additional					
		subjects required.					
		If the number of					
		patients can be					
		feasibly recruited,					
		continue to cohort					
		2 to get definitive			If Answer to		
		answer. If it is			both questions		
		not feasible to			yes, recruit		
		increase the			additional		
		sample size-		Can target engagement	subjects and		
		failure in		be established in the	confirm target		Still no robust
	Signal more variable than	sensitivity of PET		larger cohort? Is this	engagement.		target
	expected, sample size	endpoint continue		only 10 or less	Otherwise	1) invest API-3	engagement-
	increase required <10	to PD study		subjects and can these	continue to PD	and repeat dose	Stop
3)	subjects	(pSMAD2)		be feasibly recruited?	study	IPF study	development
				Is GSK3008348			
				suitable for twice daily			
		Go ahead with		dosing? Can this be			
	Signal at 30 minutes, but no	API-3 and repeat		achieved in a number			
	or inconclusive signal at 24	dosing studies in		of participants that can			
4)	hours (expected outcome)	IPF patients		be feasibly recruited?			

[figure not shown]
CONFIDENTIAL

	Interim outcomes from 204715	Impact on development of GSK3008348	Traffic lights	Question for cohort 2	Cohort 2	Cohort 2 - Positive data	Cohort- 2 negative data
							Use
		Go ahead with				Use information to	information to
		API-3 and repeat				inform dose	inform dose
		dose study with		Investigate whether		selection for	selection for
	Signal at both 30 mins and	PD assessments		lower doses can be	Investigate	repeat dosing in	repeat dosing
5)	24 hours	in IPF patients		used?	lower doses	IPF study	in IPF study

12.1.5.3. Table Explaining Programming Requirements Used at Interim Analysis

Study Decision	Description	Statistical Programming
Achieve Study Success Criteria and	Achieve Study Success Criteria	Study Success #1 $= P (log [\theta] < 0 \mid Study Data, Prior(\theta)) \ge 80\%.$ $\theta = PET1_{VT}/Pre-dose_{VT} and$ % Inhibition = (1-PET1_{VT}/Pre-dose_{VT})*100
PET Signal is Robust	PET Signal is ≥ 5% Inhibition	
Sample Size Re- estimation	Include up to 10 active additional subjects and with each additional subject evaluate Study Success Rule #2. If this rule is not met with 10 additional subjects then NO-GO, else Recruit 2 nd Cohort.	Study Success Rule #1 $= P (log [\theta] < 0 \mid Study Data, Prior(\theta)) \ge 80\%$ $\theta = PET1_{VT}/Pre-dose_{VT}$

12.1.5.4. Figure Illustrating Study Decision Making Used at Interim Analysis

12.2. Model Checking and Diagnostics for Statistical Analyses

12.2.1. General Considerations for Bayesian Analysis

- The following points are for guidance and illustration only and do not guarantee a successful model convergence. They cannot cover all eventualities and do not remove the requirement to do what is best for the specific set of observed data being modelled.
- Unless otherwise stated, data collected at screening and at unscheduled time points will not be included in the statistical analyses, i.e., only planned/scheduled post-screening data will be included except where screening data is used as baseline.
- All credible intervals reported will be 95% HPD intervals, unless otherwise specified.
- After Markov Chain Monte Carlo (MCMC) for Bayesian inference, estimated and monitored model parameters (variance components and fixed effects) were compared to corresponding estimated parameters from the linear mixed model. Confidence was gained if results were similar. Different initial values for fixed effects (but not

variance components) were used to assess convergence. Convergence for all the parameters in the model needs to be verified

• A separate seed for each MCMC chain will be set to ensure reproducibility.

12.2.1.1. Prior Distributions

Unless otherwise specified, the following will be the default approach to selecting prior distributions:

- Non-informative priors of the form Normal (0, Var=1E6) will be assigned to each fixed-effect parameter in the proposed statistical model.
- For repeated measures models, non-informative Inverse-Wishart priors of the form IW (υ, Σ) will be assigned for the Variance-Covariance (VC) matrix associated with the repeated measures timepoints. The parameter υ represents the dimension of VC (number of rows or columns) and the matrix Σ is an identity matrix of the same dimension as VC. The unstructured variance covariance structure for the repeated measurements will be assumed. In cases of non-convergence, the Toeplitz structure will be used.
 - o If there are issues with these distribution parameters, then Σ may be a diagonal matrix that uses best guesses for the residual variance at each repeated measure timepoint (or the residual estimate from fitting simple models). This only needs to be of the correct order of magnitude.
- Non-informative inverse-gamma priors of the form IG(a=2.001, b=0.001) will be used for scale parameters (variances). If these parameters do not lead to convergence, then choose "a" small and "b" smaller than the expected standard deviation.

It is good practice to ensure that each prior distribution is visualized to ensure it appears sensible, i.e., that it allows parameter values that generate clinically plausible response values and that it is truly non-informative over the region of the likelihood function where the data lies.

Note:

• The Gamma(a,b) density function takes the form

$$p(u) = \frac{b(bu)^{a-1}e^{-bu}}{\Gamma(a)}, u > 0$$

The mean is a/b and the variance is a/b^2 .

• The IG(a,b) density function takes the form

$$p(u) = \frac{b^a u^{-(a+1)} e^{-b/u}}{\Gamma(a)}, u > 0$$

The mode is b/(a+1), the mean is b/(a-1), if a>1, and the variance is $b^2/[(a-1)^2(a-2)]$, if a>2.

• There is no requirement to formally report the prior visualisation outputs.

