## 10.3. Statistical Analyses

### 10.3.1. Pharmacodynamic Analyses

Endpoint	Statistical Analysis Methods
Volume of distribution [ $V_T$ ] in whole lung, not corrected for air volume	The logarithm of the $\alpha\beta 6$ -associated PET signal as measured by $V_T$ will be analysed assuming that it follows a normal distribution. The mean or median signal level pre- and post-dose, as appropriate depending on the posterior distribution, along with the median difference post-dose – pre-dose, will be estimated and the corresponding 95% credible intervals will be produced. The posterior probability that the true difference in the logarithm of $\alpha\beta 6$ -associated PET signal post-dose vs pre-dose is less than 0 will be calculated. Non-informative priors will be used for all the parameters in the statistical model.
Secondary	Will be described in the reporting and analysis plan (RAP)
Exploratory	Will be described in the RAP

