7.1.5.1. Statistical Methodology Specification

Endpoint / Variables

V_T (whole lung, not corrected for air volume), at 1000 mcg GSK3008348

Timepoint

• The primary timepoint of interest is the 30 minutes post-dose PET scan timepoint.

Model Specification

- The distribution of V_T will be explored using graphical approaches. It is likely that this follows a log-normal distribution in which case the logarithm transformation will be applied, and a normal distribution assumed for log (V_T).
- Only data from those subjects receiving 1,000 mcg GSK3008348 will be included in the primary analysis (i.e., no placebo data will be included) in Cohort 1.
- The three PET scans per subject will be denoted by Pre-dose (Baseline PET in Period 2), PET1 (Period 2, Day 1, 30 minutes PET after dose of GSK3008348, allowable time window is 20-60 mins) and PET2 (Period 2, Day 2, 24 hours PET after dose of GSK3008348, allowable time window is 14-28 hrs).
- The mean of the normal distribution will be allowed to vary per post-dose scan timepoint by defining the 3-dimensional array parameter ResponsebyVisit as follows:
 - o ResponsebyVisit[1] = mean of log (Response) at 'Pre-dose'
 - ResponsebyVisit[2] = mean of log (Response) at 'PET1'
 - ResponsebyVisit[3] = mean of log (Response) at 'PET2'
- In addition, the following 3 dimensional array parameter ResponseRatio will also be created:
 - o ResponseRatio[1] = PET1/Pre-dose
 - o ResponseRatio[2] = PET2/Pre-dose
 - o ResponseRatio[3] = PET2/PET1
- The inclusion of covariates Age, Sex, Baseline % predicted FVC, and Baseline % predicted DLCO (baseline from Period 2) will be explored in a sequential manner and included in the model if the 95% HPD credible interval for the corresponding regression coefficient excludes 0.
- This endpoint will be analysed using Bayesian inference assuming non-informative priors of the form N(mean=0, SD = 1000) for all regression coefficients in the model.
- An unstructured 3x3 variance-covariance matrix will be assumed to model the
 dependency between log (V_T) in the three PET scans. If the model fails to converge
 then additional structures such as the Toeplitz structure should be explored. Details
 of the prior distributions are presented in Section 12.2.

Model Checking & Diagnostics

• Refer to Section 12.2: Model Checking and Diagnostics for Statistical Analyses.

Model Results Presentation

- Plots of the posterior samples (chains) will be produced for all the parameters in the model as listings.

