- Posterior density plots for V_TRatio;

- o PET1/Pre-dose
- o PET2/Pre-dose
- o PET2/PET1

will be produced.

- The adjusted posterior median values of V_TRatio (PET1/Pre-dose, PET2/Pre-dose and PET2/PET1) will be presented in tabular form together with the corresponding standard deviations and 95% HPD credible intervals.
- Plots of individual subject data for PET1/Pre-dose, PET2/ Pre-dose and PET2/PET1 will be superimposed with the adjusted posterior median values of PET1/Pre-dose, PET2/Pre-dose and PET2/PET1 respectively. These plots should also include the corresponding 95% HPD credible intervals for PET1/Pre-dose, PET2/Pre-dose and PET2/PET1.
- The posterior probability that the true ratio PET1/Pre-dose is less than 1 will be calculated.

Subgroup Analyses

None

Sensitivity and Supportive Analyses

• Following review of the data, additional analyses may be conducted to further support the primary statistical analysis, if deemed appropriate. The posterior probability that the true ratio PET1/Pre-dose is less than 0.9, 0.8, 0.7 and 0.6, as appropriate depending on the observed data, will also be calculated. If the PP and ITT populations differ, the same statistical analysis using the ITT population will also be conducted.

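### The SAP's default covariance prior (inverse-Wishart, 3 df, identity scale) is not non-informative for five participants' log V_T: if it is used, the 80% success rule needs a 23.3% observed fall instead of about 6%

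*SAP*

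**What the plan says.** Protocol 10.3.1 commits the primary analysis to this: "Non-informative priors will be used for all the parameters in the statistical model". SAP 2.1 reports no deviation from the protocol's analysis.

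SAP 7.1.5.1 uses only the participants on 1,000 mcg. It states "An unstructured 3x3 variance-covariance matrix will be assumed to model the" dependence among the three scans, and refers to Section 12.2 for priors. Section 12.2.1.1 gives the default for that matrix: inverse-Wishart with degrees of freedom equal to the dimension (3), where "the matrix Σ is an identity matrix of the same dimension as VC".

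The same section offers a way out: "If there are issues with these distribution parameters, then Σ may be a diagonal matrix" built from "best guesses for the residual variance at each repeated measure timepoint", or from the residual of a simple model, correct only to an order of magnitude. It also calls it good practice to look at each prior and confirm that it is non-informative where the data lie. Section 12.2.1 describes its points as guidance that "do not remove the requirement to do what is best for the specific set of observed data being modelled". It also reports that the Bayesian estimates "were compared to corresponding estimated parameters from the linear mixed model".

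**The concern.** A scale matrix is weak or strong only relative to the variance of the data. Log V_T is expected to vary by tenths of a log unit or less within a participant, so unit variance is very large, and five participants cannot outweigh it.

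The final analysis is still to be run under this text. If the default is followed, the reported probability that the ratio is below 1 and its 95% interval would mainly describe the prior. So would the supportive probabilities that the ratio is "less than 0.9, 0.8, 0.7 and 0.6, as appropriate depending on the observed data". The distortion runs both ways: support for any fall is understated, and support for falls larger than the one observed is overstated.

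**Working it through.** **Inputs.** Protocol 10.1: five actives; success if the posterior probability of θ < 0 is at least 80%; SD 0.15 (95% CI 0.099 to 0.34); minimum detectable effect 6.2%; 86% success at a true 14% fall. SAP 7.1.5.1 and 12.2.1.1: means with Normal priors of variance 1E6 (effectively flat); covariance IW(3, identity).

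**Assumption.** Reading A takes 0.15 as the SD of the log ratio. Reading B takes it as the SD of one scan, so the log-ratio SD is 0.15 × √2 = 0.212. Scans are complete and no covariate enters.

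**1. The protocol's figure.** Under a flat prior the mean log ratio is t with 4 df and scale 0.15/√5 = 0.0671. The fall needed is 1 − exp(−0.941 × 0.0671) = 6.1%. An SD of 0.152, which rounds to 0.15, gives 6.2%. Reading B gives 8.5%, so A fits better. Success at a true 14% fall is 90% (noncentral t). The stated 86% is only approached by variants: 86.9% with a shifted t, or 85.1% to 85.8% when averaging over uncertainty in the SD. Nothing below depends on this.

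**2. The SAP default.** Integrating out the means gives IW(3 + 5 − 1, Σ + SS), where SS is the matrix of sums of squares. Let s0 be the diagonal of Σ and SS_d the sum of squares of the five log ratios about their mean. The variance of the PET1 minus Pre-dose contrast is inverse-gamma(5/2, (2·s0 + SS_d)/2). The mean log ratio is therefore t with 5 df and

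scale² = (2·s0 + SS_d)/25.

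With identity, s0 = 1. Under A, SS_d = 4 × 0.0225 = 0.09. The prior share is 2/2.09 = 96% (B: 2/2.18 = 92%). The scale is √(2.09/25) = 0.289, and the fall needed is 1 − exp(−0.920 × 0.289) = 23.3%. Over SDs of 0.099 to 0.34 this moves only from 23.1% to 25.1%, while the flat-prior figure moves from 4.1% to 13.3%. Identity is its own inverse, so reading Σ as scale or inverse scale makes no difference.

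**3. Operating figures, A (B).** The fallback rows use the SAP's diagonal Σ in two ways. The within-subject variance is half the log-ratio variance, s0 = 0.01125 (0.0225). The total variance at a scan adds an assumed between-subject SD of 0.3, s0 = 0.09 + 0.01125 = 0.101 (0.1125).

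| Prior | Observed fall needed | Success at true 14% fall | Success at no effect |
|---|---|---|---|
| Flat | 6.1% (8.5%) | 90% (75%) | 20% (20%) |
| IW(3, identity) | 23.3% (23.8%) | 4% (10%) | below 0.01% (0.2%) |
| Fallback, within-subject | 6.0% (8.4%) | 91% (75%) | 19% (19%) |
| Fallback, total | 9.5% (11.0%) | 78% (64%) | 7% (11%) |

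The documents give no between-subject SD. Over 0.1 to 0.5, the last row's threshold runs from 6.5% to 13.4% (8.7% to 14.5%).

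**4. Reported quantities at an observed 14% fall (A).** P(ratio < c) is the t distribution function at (ln c − ln 0.86)/scale.

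| Quantity | Identity | Flat |
|---|---|---|
| P(ratio < 1) | 0.69 | 0.96 |
| P(ratio < 0.8) | 0.41 | 0.17 |
| P(ratio < 0.7) | 0.25 | 0.02 |
| 95% HPD interval | about 0.32 to 1.61 | 0.71 to 1.03 |

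**5. Check.** Gibbs sampling of the full 3x3 model under identity gave P(ratio < 1) = 0.690 at an observed 14% fall (closed form 0.688) and 0.797 at 23.3%.

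**The case against.** The strongest reply is that identity is only a starting point. The section is guidance, the analyst must still do what suits the data, and the SAP supplies both a criterion (non-informative where the data lie) and an action (replace Σ). Identity plainly fails that criterion. The mixed-model comparison would also expose it: the posterior mean log-ratio variance under identity is (2.09/2)/1.5 = 0.697, against 0.0225 in the data, a 31-fold gap (16-fold under B). With a within-subject residual, the fallback restores the protocol's threshold.

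Much of this stands, and it narrows the point. But the replacement is permissive, the prior check is described as good practice and need not be reported, and nothing gives a numerical trigger. The MCMC diagnostics in 12.2.1.3 test sampling, not prior influence. The fallback wording also covers two different variances, and one of them leaves the threshold at 9.5%.

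The planned outputs help too: Table 3.3 footnotes the priors, Figure 3.1 shows raw data with unadjusted intervals, and Listing 38 carries the raw model output. A careful reader could detect the problem, but the headline inference would still be wrong.

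A reader might infer that the interim declaration of success was unsound. The documents do not support that. They do not say which Σ was used. If it was identity, success also follows under the flat prior, whose threshold is lower for any log-ratio SD below about 1.27. If it was another Σ, the default had already been set aside. A reader might also infer that false success is inflated; under identity it is reduced.

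**Conclusion.** The default is wrong as written. IW(3, identity) is not non-informative for this endpoint, and it conflicts with Protocol 10.3.1 and with the operating figures in Protocol 10.1. If used, it moves the success threshold from 6.1% to 23.3% (B: 8.5% to 23.8%) and success at a true 14% fall from 90% to 4% (B: 75% to 10%).

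The conflict concerns the covariance prior only. Protocol 10.1 and 10.3.5.1 ask for a non-informative prior on θ, and the SAP's Normal priors on the means meet that.

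The harm is confined to the final primary probability, the intervals and the supportive probabilities, and arises only if the default is actually run. Cohort 2 was not conducted, so consequences for it are moot. The figures rest on five complete actives, no covariates and an SD near 0.15, though the identity threshold barely depends on that SD.

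**What to change.** For the final analysis, keep the joint 3x3 model, since it also supplies the secondary results. In SAP 12.2.1.1, replace identity with a mandatory diagonal Σ set to the within-subject residual variance of log V_T from a simple model, for example a random-intercept model. An equivalent prior shown to be non-informative for the log-ratio contrast would also do. Say explicitly that the total variance at each scan is not meant.

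If the residual is estimated from the same Pre-dose and PET1 scans, s0 = SS_d/8, so scale² = (SS_d/4 + SS_d)/25 = SS_d/20. That is the flat-prior value, so using the data twice changes little here beyond 4 df becoming 5.

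State which Σ the interim used. Report P(ratio < 1), the 95% HPD intervals and the supportive probabilities under both the new prior and IW(3, identity).

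The cost is one SAP line and a rerun, with no new participants or data. The drawback is that SAP 1.1 dates the amendment after the interim, so the change is data-aware. It also makes success easier: success at no effect rises from below 0.01% (B: 0.2%) to about the 20% that the protocol's rule implies. Justify it only by the protocol's pre-stated non-informative prior, and show both results.
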